Test the acceptability and feasibility of our brief motivational interview intervention to facilitate advance care planning (ACP) conversation on older adults with serious co-morbid illness being discharged from the emergency department (ED) and interview the participants to understand their perception and collect patient-reported outcomes data after leaving the ED.

Hypotheses

- a) $\geq 80\%$ of clinicians will find it acceptable to conduct this interview in the ED for appropriate patients;
- b) $\geq 80\%$ of patients will find the interview respectful to patient-oriented needs;
- c) $\geq 25\%$ of participants will have reported completing ACP conversation with their primary outpatient clinician at three month after leaving the ED.

Methodology

We will pilot test (Part I) the intervention to ED patients and interview 15 to 25 participants (depending on theme saturation) immediately following the intervention to explore how they perceived the intervention. After the intervention is administered, they will be asked to complete a Likert scale survey about acceptability. Additionally, we will collect pre-/post-intervention patient-centered outcome data (Part II) in-person at the time of intervention and via phone interview at three months after the ED visit for 100 patients.

III. SUBJECT SELECTION

Trained RAs will recruit the subjects using the inclusion and exclusion criteria (**Table 2**). We will use convenience sampling for this study. Each morning when a trained EM physician evaluates patients in the ED observation unit, the trained RAs will ask the physician to identify potential subjects based on inclusion and exclusion criteria.

| Inclusion | Exclusion |
|-------------------------------|--------------------------------------------------|
| ≥ 65 years of age | Acute physical or emotional distress |
| English-speaking | Determined by EM physician not to be appropriate |
| Capacity to consent | Clearly documented goals for medical care** |
| AND ≥ 1 Serious illness* | Already enrolled in this study |

*New York Heart Association stage 3 or 4 heart failure, oxygen-dependent chronic obstructive lung disease, chronic kidney disease on dialysis, and metastatic cancer. **MOLST, medical order for life sustaining treatment.

IV. SUBJECT ENROLLMENT

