There are two subject types in this study – ED clinicians and ED patients. ED clinicians (attending physicians and physician assistants) will be recruited to train in and administer the proposed intervention on ED patients. After the intervention is administered, they will be asked to complete a Likert scale survey about acceptability. Clinicians will be asked to participate voluntarily. The PI will make an announcement at the faculty / physician assistant meetings and hand out the study information sheet. ED patients will be recruited to be interviewed after the intervention to learn their perception of the intervention. Upon identification of the

potential subject, the trained RAs will approach the potential subject to explain the study and ask about their willingness to participate. Once the eligible subject agrees to participate, the PI will consent the patient to enroll. After the trained RAs explain the study, the subjects will have time to think about the enrollment until the PI physically arrives in the ED. The PI will review all study elements again with the subjects to ensure understanding of the study. Upon enrollment, the trained physician responsible for the care of the patient will administer the intervention. When a trained physician is not on duty in the ED observation unit, the PI will administer the intervention.

There will be no other methods of recruiting for this study. Since this is a single-armed, pre-/post-intervention assessment study, there will be no treatment assignment or randomization.

V. STUDY PROCEDURES

There will be two distinct parts of the study: acceptability study (Part I) using qualitative interviews to explore the patient’s perception of the intervention and quantitative assessment of clinician’s acceptability rating, and feasibility study to measure patient-reported outcomes (Part II) after leaving the ED for future randomized clinical trial. The timing of proposed data collection is shown on Table 3.

| Table 3 Timing of Proposed Data Collection and Instruments | | | | |
|------------------------------------------------------------|------------|--------------------------------------------------------|-----------------------|--------------------------------------------------------|
| Study Part | Subjects | Pre-Intervention | Post-Intervention | Three Month Follow-up |
| Part 1 | Clinicians | | Acceptability Survey | |
| | Patients | | Qualitative Interview | |

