| Part 2 | Patients | ACP Engagement Survey QUAL-E Survey IES-R Survey | | ACP Engagement Survey QUAL-E Survey IES-R Survey |

Part I: Acceptability Study

We will conduct in-depth, semi-structured interviews to understand patient’s perception of the intervention after its administration by a trained ED clinician. We anticipate to interview 15 to 25 patients, until thematic saturation of their perception is reached. Further, we will assess clinician acceptability by administering a Likert scale survey.

Measurements

Patient Perception Assessment: The PI and the trained RA will conduct the semi-structured interviews. The following domains will be explored: beliefs about formulating and communicating goals of care, experience of the ED intervention, and attitude towards further patient education about how to formulate goals of

care. Both the administration of BMI intervention by a clinician and subsequent qualitative interview of the participants will be video-recorded to ensure fidelity of the intervention administration and accurate capturing of their inputs.

Clinician Acceptability Assessment: Immediately after the clinician completes the encounter, we will ask to fill out an in-person survey to rate acceptability (Likert scale, 1 – not acceptable, 2 – somewhat unacceptable, 3 – neutral, 4 – somewhat acceptable, and 5 – acceptable).

Outcome Our primary outcome for the patient perception assessment of the study is to identify a recurring theme that illustrates the patient perception of the intervention. Our primary outcome for the physician assessment of the study is the proportion of administering clinicians who found the rating to be somewhat acceptable (4) or acceptable (5). Secondary outcomes are the time to administer the intervention and how often the 4 intervention components are appropriately completed.

Part II: Feasibility Study

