We hope that our intervention will allow EM clinicians to reach many older adults with serious illness presenting to the ED and guide them to formulate their goals for medical care. Such intervention will allow clinicians to align the future medical care towards end of life to match patients' values and preferences.

IX. MONITORING AND QUALITY ASSURANCE

The PI will be solely responsible for monitoring of safety, adverse events, protocol deviations, and outcomes. The data safety will be monitored by the PI on weekly basis, who is solely responsible for determining whether the research should be altered or stopped. The PI will be aware of every patient who is recruited and enrolled in the study. All data obtained in this study (video-recorded interviews of the participants and responses to the surveys by both clinicians and participants) will be stored in a secure Partners shared drive of the PI. As soon as the opportunity is available, the obtained data will be anonymized and removed of personal health information. All participants and clinicians will be de-identified and assigned research subject IDs (e.g. clinician 1). Only the study staff will have access to information that can link the subject IDs with the personal health information, which will be saved in the secure shared drive.

The PI will be aware of every subject enrolled in this study. Therefore, he is able to monitor for adverse events, such as unexpected emotional distress, and address them clinically using his clinical communication skills. Further, the PI will inform the IRB of any adverse events using standard procedures.

As stated earlier, the PI will be solely responsible for the adherence to the IRB-approved protocol. The PI will be checking the adherence on every enrollment (especially because he will physically be there).

X. REFERENCES

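### The PI may both deliver the intervention and interview the same patient about it straight afterwards; a one-sentence interviewer rule would separate the two roles

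*Protocol*

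**What the plan says.** Four provisions of the Protocol bear on this.

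- **Delivery (IV. Subject Enrollment).** By default, the treating physician who has been trained delivers the intervention. The exception is: "When a trained physician is not on duty in the ED observation unit, the PI will administer the intervention". No limit is set on how often this may happen. The same section has the PI obtain consent from each patient.
- **Interviewing (V. Study Procedures, Part I, Measurements).** "The PI and the trained RA will conduct the semi-structured interviews". One of the domains is how the patient experienced the intervention. No rule allocates patients between the two interviewers.
- **Timing (II. Specific Aim, Methodology).** The plan is to "interview 15 to 25 participants (depending on theme saturation) immediately following the intervention to explore how they perceived the intervention".
- **Presence (IX. Monitoring and Quality Assurance).** "The PI will be checking the adherence on every enrollment (especially because he will physically be there".

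The opening of Part I in section V describes the interviews as taking place "after its administration by a trained ED clinician". Section IV contrasts a trained physician with the PI, so the text does not settle whether patients treated by the PI belong in the interview sample.

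The safeguards in sections V and VI are video recording of both delivery and interview, independent coding by the PI and the RA, a third coder for disagreements over themes, and an additional researcher for disputed quotes and themes.

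**The concern.** The Part I primary outcome on the patient side is the recurring theme in how patients perceived the intervention. Its value to the later randomized trial lies in candid criticism. A patient questioned by the person who, minutes earlier, led a sensitive conversation has a social reason to be polite. The resulting error has a predictable direction, towards favourable views, and it arises when the patient answers. Coding can only work with what was said.

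This is a matter of study conduct. The Protocol itself fixes who delivers and who interviews, and no later analysis plan could repair an answer given under those conditions.

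A lesser, related matter is that section V lists two measures without reference to who delivered: "Secondary outcomes are the time to administer the intervention and how often the 4 intervention components are appropriately completed". Section I says that what is lacking is an intervention for physicians without extensive communication training, whereas section VII says that the PI has such training. It would therefore help to be able to show these measures by deliverer.

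**Working it through.** The Protocol gives no figure for this overlap, so there is none to reproduce. The check has two steps.

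**Step 1: do the provisions allow the overlap?** Section IV lets the PI deliver. Section V lets the PI interview. Section II leaves almost no gap between the two. Section IX has the PI present at every enrollment, so the PI is at hand for the interview. No passage excludes the combination and none demands it. The overlap is permitted, and its frequency is left to chance and staffing.

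**Step 2: how large could it be?**

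Inputs:
- N = 15 to 25 interviews (sections II and V). The Sample Size paragraph of section VI gives 10 to 25; the range stated in the other places is used here.
- s = share of interviewed patients to whom the PI delivered. Not stated; assumed 10% to 20%.
- q = share of those patients whom the PI interviews. Not stated; assumed 0.5 if the interviewers divide the work, and 1 if they interview jointly.

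Formulas, treating patients as independent:
- Expected overlapping interviews = s × q × N
- Chance of at least one = 1 − (1 − s × q)^N

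| s | q | N | Expected overlap | Chance of at least one |
|---|---|---|---|---|
| 0.10 | 0.5 | 15 | 0.75 | 1 − 0.95^15 = 54% |
| 0.10 | 0.5 | 25 | 1.25 | 1 − 0.95^25 = 72% |
| 0.20 | 0.5 | 15 | 1.5 | 1 − 0.90^15 = 79% |
| 0.20 | 0.5 | 25 | 2.5 | 1 − 0.90^25 = 93% |
| 0.10 | 1 | 15 | 1.5 | 1 − 0.90^15 = 79% |
| 0.10 | 1 | 25 | 2.5 | 1 − 0.90^25 = 93% |
| 0.20 | 1 | 15 | 3 | 1 − 0.80^15 = 96% |
| 0.20 | 1 | 25 | 5 | 1 − 0.80^25 = over 99% |

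The event counted is PI delivery together with a PI interview of the same patient. PI delivery alone is not the problem. The chance of at least one overlap shows how likely the situation is to arise; it does not measure bias. As a share of the sample, the expected overlap is s × q: 5% to 10% if the interviews are divided, and 10% to 20% if they are joint.

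**The case against.** The case on the other side is substantial.

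- **The overlap may be rare.** Screening occurs "Each morning when a trained EM physician evaluates patients in the ED observation unit". If trained there means trained in this intervention, a trained physician would normally be on duty and the fallback would seldom be used. The description of the interviews as following delivery by a trained ED clinician could even exclude PI-delivered patients. Both readings are possible and neither is stated. If the overlap is rare, the rule costs almost nothing.
- **One or two interviews will hardly determine a recurring theme.** This stands, and it is why the point is not graded higher.
- **Safeguards exist.** Video allows any influence to be inspected, and the RA codes independently. This helps, but it all acts after the patient has answered, and the PI is also one of the two coders.
- **The RA is not a neutral party.** RAs recruit the patients, so changing the interviewer reduces the social pressure without removing it. This also stands.

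A reader might infer more than the text supports, in three ways.

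- **Hypothesis (b).** The aim that at least 80% "of patients will find the interview respectful to patient-oriented needs" might seem open to being tipped by a few polite answers. No passage turns the interviews into a proportion: their outcome is a theme and their analysis is thematic coding. The Likert survey mentioned in section II may or may not be for patients. How (b) is measured is a different question.
- **Time and component completion.** These might be called wrongly defined because PI encounters are not excluded. Restricting or stratifying them is an analysis choice that a statistical analysis plan could make, and that plan is not at hand.
- **Clinician acceptability.** The proportion most naturally covers the recruited clinicians, so there is no good ground for saying that the PI's own rating inflates it.

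**Conclusion.** The point holds as a cheap improvement of minor to moderate weight. The Protocol allows the PI to interview patients about an intervention that the PI has just delivered, and none of its safeguards separates the two roles. The likely effect is a tilt of the Part I patient-perception theme towards favourable views.

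The size rests wholly on assumed values of s and q. With divided interviewing, it is about 0.75 to 2.5 of 15 to 25 interviews; with joint interviewing, it is 1.5 to 5. A lower PI share would shrink these figures in proportion.

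The Protocol does not support the claim that the PI routinely assesses the PI's own work, or that the pilot is invalid. Part II is not affected by this route, since section V has trained RAs administer its instruments. The mismatch between the four components to be scored and the six numbered steps of Table 1 is a separate matter and carries no weight here.

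**What to change.** 1. In the Patient Perception Assessment paragraph of section V, state that any patient to whom the PI delivered the intervention is interviewed by the trained RA without the PI. This also settles that such patients may be in the interview sample. If they are meant to be excluded, say that instead.
2. Record the deliverer for each encounter, so that administration time and component completion can be shown by deliverer.

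This takes two sentences and one data field, and uses staff already named. The downside is that the RA must be available for an interview whenever the PI delivers.

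### The clinician acceptability rating may be inflated by social desirability, because it is an identifiable in-person rating taken by the study team with no private completion described

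*Protocol*

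**What the plan says.** - **Target and outcome.** Section II, hypothesis (a), expects at least 80% "of clinicians will find it acceptable to conduct this interview in the ED for appropriate patients". Section V, Part I, takes as the primary outcome on the clinician side the proportion of administering clinicians who give a 4 or a 5 on a five-point scale where 3 is neutral.
- **Mode and timing.** Section V, Clinician Acceptability Assessment, sets the timing as directly after the encounter and the mode as follows: "we will ask to fill out an in-person survey to rate acceptability". The collector is only "we".
- **Recording.** Section V, Part I, has the delivery of the intervention video-recorded to check fidelity.
- **Recruitment of raters.** Section IV makes taking part a free choice for clinicians and describes how they are approached: "The PI will make an announcement at the faculty / physician assistant meetings and hand out the study information sheet".
- **The PI on site.** Section IV has the PI come to the ED to take each patient's consent. Section IX adds: "The PI will be checking the adherence on every enrollment (especially because he will physically be there"). In Part I, "The PI and the trained RA will conduct the semi-structured interviews", which Section II places directly after the intervention.
- **The PI as administrator.** Section IV lets the PI deliver the intervention when no trained physician is working in the observation unit.
- **Data handling.** Section IX stores the survey responses of clinicians and patients on the PI's secure shared drive. They are anonymized when the opportunity arises, and study staff hold the link to the subject IDs. The PI alone monitors safety, adverse events, deviations and outcomes.

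**The concern.** The outcome is one subjective item with no comparator, and it is cut between neutral and somewhat acceptable. A rater who is neutral but polite needs to move only one point to change category. The conditions of collection all lean the same way: volunteers approached by the PI, a delivery that has just been recorded, a form requested in person by the team that developed the intervention, and a name still attached to the answer. Later removal of names protects storage. It does not protect the moment of rating.

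At stake is whether hypothesis (a) is declared met. The study is meant to inform the design of a randomized trial, so an acceptability figure that is too high would be carried into that trial's planning.

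**Working it through.** **1. Is there a plan figure to reproduce?** No. The protocol gives no number of clinicians, no test and no power for this outcome. The Part I numbers in Section VI are for the interviewed patients. The check is therefore a reading of the text, followed by an illustration on assumed values.

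**2. Sequence at one Part I encounter, from Sections II, IV, V and IX.**

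| Step | Who is stated to be involved |
|---|---|
| Eligibility and approach | Trained RAs and the physician |
| Consent | PI, in person |
| Intervention, video-recorded | Trained clinician, or the PI if none is on duty |
| Clinician survey, immediately afterwards | Clinician; requested by an unnamed "we" |
| Patient interview, immediately after the intervention | PI and RA |
| De-identification | Later |

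The PI is stated to be on site around the time of the rating. No sentence places the PI beside the clinician during it. No sentence provides for private, sealed or electronic completion either.

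**3. How sensitive is the 80% line? (Assumed values only.)** Let *p* be the true share who would rate 4 or 5, and *s* the share of all other raters who move up to 4. The observed share is *p* + (1 − *p*)*s*. It reaches 0.80 when *s* = (0.80 − *p*)/(1 − *p*):

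| *p* | *s* needed |
|---|---|
| 0.60 | 0.20/0.40 = 0.50 |
| 0.65 | 0.15/0.35 = 0.43 |
| 0.70 | 0.10/0.30 = 0.33 |
| 0.75 | 0.05/0.25 = 0.20 |

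This lets every rating of 1, 2 or 3 move. If only neutral raters move, and they are a share *q* of all raters, the requirement is (0.80 − *p*)/*q*. At *p* = 0.70 that is 0.10/0.30 = 0.33 if all the rest are neutral, 0.10/0.20 = 0.50 if two thirds of them are, and 0.10/0.10 = 1.00 if one third are. The table is therefore the most sensitive case.

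**4. Chance of observing at least 80%.** This is a binomial upper tail with independent raters. The number of clinicians is assumed, since the protocol gives none.

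| Share rating 4 or 5, true or shifted | 10 clinicians (8 or more) | 20 clinicians (16 or more) |
|---|---|---|
| 0.70 | 0.38 | 0.24 |
| 0.75 | 0.53 | 0.42 |
| 0.80 | 0.68 | 0.63 |
| 0.85 | 0.82 | 0.83 |

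A shift from 0.70 to 0.80 would raise the chance of meeting the target from 0.38 to 0.68 with 10 clinicians, and from 0.24 to 0.63 with 20.

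**5. PI-administered encounters.** The outcome is defined over administering clinicians, and the PI can be one. The text does not exclude the PI's own rating. Suppose the PI counts once and rates 4 or 5. With 10 raters in all, 7/9 = 77.8% among the others becomes 8/10 = 80%. With 20, 15/19 = 78.9% becomes 16/20 = 80%.

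**The case against.** The strongest reply is that the decisive fact is missing. A reader might infer that clinicians rate the intervention under the PI's eye, while being checked. The protocol does not say so. Section IX ties the PI's presence and adherence check to enrollment, which comes before the intervention, and in Part I the PI may already be with the patient when the clinician fills in the form. A reader might also infer that the PI promotes the intervention to colleagues, but the text describes an announcement, an information sheet and voluntary participation. These points stand, and the stronger readings are not made here.

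Three more replies deserve an answer.

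- **Immediate collection limits recall error and missing forms.** This is correct. The timing is not a fault, and the fix keeps it.
- **The shift figures are assumptions.** This is also correct. They show how sensitive the 80% line is and do not estimate any bias.
- **Little depends on the result, because this is a pilot with no test or go/no-go rule attached to the 80% figure.** That lowers the weight of the point. It does not remove it, since the protocol names this as a primary outcome with a numerical hypothesis.

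The mode of collection is also not a detail left open for an analysis plan. The protocol itself chooses an in-person survey, and later de-identification does not answer the objection to that choice.

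**Conclusion.** The point holds as a risk. The primary clinician outcome may be inflated by social desirability, because an identifiable rating is requested in person by an unnamed member of the study team. The PI of that team recruited the raters, is on site at each enrollment and holds the data, and no private completion is described. The direction is predictable, towards meeting hypothesis (a).

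The size is unknown and cannot be derived from the protocol. It would be tempting to conclude that the result is pushed to 80%. The document does not support that: nothing in it shows that any rating would move, and smaller shifts can leave the target missed. For example, from an assumed 65%, moving a quarter of the rest gives 0.65 + 0.35 × 0.25 = 0.74. Nor does the protocol say that the PI's own ratings will be counted, only that they are not excluded.

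This is a cheap improvement to make before Part I results are interpreted. It is not an error that invalidates the study.

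**What to change.** 1. **Section V, Clinician Acceptability Assessment.** Keep the immediate or same-day timing. Replace the in-person survey with a form that the clinician completes privately, on sealed paper or by electronic link, under a study ID, and returns to a named RA without the PI present.
2. **Section IX.** State that individual clinician ratings are kept where the PI cannot open them and are not shown to the PI until Part I closes. Because Section IX makes the PI responsible for monitoring outcomes and stores the surveys on the PI's drive, write this as an explicit exception. Safety and adverse-event monitoring is unaffected.
3. **Section V, Outcome.** Exclude from the 80% proportion any rating from an encounter in which the PI administered the intervention.

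The cost is a few changed sentences, a link or a stock of envelopes, and a restricted folder managed by existing RAs. The downside is a few late or missing forms, whose number should be reported beside the proportion.
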